10.2.4 INTERIM ANALYSIS AND STOPPING RULES

This study will consist of 2 stopping rules: one for futility (lack of efficacy) and another for excess toxicity.

For futility, we will follow the stopping rule based on the Simon's 2-stage design with the minimax criteria. Specifically, if there is no response among the first 7 patients after receiving 2 cycles of study agent, the arm will not proceed to the second stage.

[figure not shown]
For excess toxicity, we will suspend enrollment if the lower 90% confidence interval for Grade 3 or higher treatment-related toxicity exceeds 30% (considered acceptable dose-limiting toxicity (DLT) incidence). We will then conduct a comprehensive toxicity evaluation and consult with the Knight Cancer Institute's Data and Safety Monitoring Committee for guidance on possible modifications of the protocol, including termination of one or more of the arms, dose modification, and/or changes in eligibility criteria.

10.2.4.1 Safety Stopping Rule

Temporarily suspend the trial if the number of patients with DLT is equal to or greater than the number shown below:

N	4	5	6	7	8	9	10	11	12	13	14	15	16	17	18	19	20
DLT	3	4	4	5	5	5	6	6	7	7	7	8	8	9	9	9	10

The safety boundary is also shown in **Figure 4. Toxicity stopping rule**. Figure 4.

10.3 SAMPLE SIZE, POWER, ACCRUAL RATE AND STUDY DURATION

10.3.1 SAMPLE SIZE AND POWER

The sample size for each group was derived according to the 2-stage design with minimax criteria using the following parameter settings: 1) 80% power; 2) 5% significance level; 3) historical response rate of 5% (poor response), and 4) desired response rate of 30% (promising response).²¹ The sample size and power analyses were conducted using PASS 14 software (<http://www.ncss.com/software/pass/>). Based on the expected accrual rate of 14 participants per year, we anticipate this trial to take 36 months (24 months of accrual and 12 month of minimum follow-up).

10.4 HANDLING OF MISSING DATA

Missing data will not be imputed. Whenever possible, the analysis will be conducted using all available data. Missing data will be reported in the descriptive summary, and it will be noted if some subjects are excluded from the analysis due to missing data.

11. CLINICAL MONITORING

11.1 OHSU KNIGHT CANCER INSTITUTE DATA & SAFETY MONITORING PLAN

This study is under the oversight of the Knight Cancer Institute's DSMC as described in the Knight institutional DSMP. The Knight DSMP outlines the elements required to ensure the safety of clinical trial participants, the accuracy and integrity of the data and the appropriate modification of cancer-related clinical trials for which significant benefits or risks have been discovered or when the clinical trial cannot be successfully concluded. The Knight DSMP also describes the methods and procedures for ensuring adequate oversight of cancer-related research at OHSU.

As described in the Knight DSMP, regardless of a trial's risk level and any specific Knight oversight in place, the Investigator is singularly responsible for overseeing every aspect of the design, conduct, and final analysis of his/her investigation.

The Knight DSMC will review and monitor study progress, toxicity, safety and other data from this study. Information that raises any questions about participant safety or protocol performance will be addressed by the Investigator, statistician and study team. Should any major concerns arise, the Knight DSMC may recommend corrective action and determine whether or not to suspend the study.

The Knight DSMC will review each protocol every 6 months, but may occur more often, if required, to review toxicity and accrual data (please refer to Knight DSMP for additional details on audit frequency). The Knight DSMC will review accrual, toxicity, response and reporting information. Information to be provided to the DSMC may include: participant accrual; treatment regimen information; AEs and SAEs reported by category; summary of any deaths on study; audit results; and a summary provided by the study team. Other information (e.g. laboratory values) will be provided upon request.

11.2 CLINICAL DATA & SAFETY MONITORING

Monitoring visits will be performed during the study to ensure that the rights and well-being of human participants are protected, that the reported trial data are accurate, and that the conduct of the trial is in compliance with the protocol, GCP, and applicable regulatory requirements.

Details of monitoring activities, including designation of assigned monitoring entities, scope of monitoring visits, timing, frequency, duration of visits, and visit reporting, will be included in a separate TSMP that is reviewed and approved by the Knight DSMC and IRB according to the DSMP v5.1.

The Investigator agrees that the monitor will be permitted to conduct monitoring visits at appropriate intervals. The Investigator agrees to provide all relevant information and documentation as requested by the monitor, including access to all original study documents and source data, including access to electronic medical records and/or source documents if necessary.

The monitor will conduct source data review and verification as outlined in the TSMP, and following each visit will generate a report summarizing the visit findings.

Regardless of monitoring entity, the Sponsor is ultimately, singularly responsible for overseeing every aspect of the design, conduct, and final analysis of the investigation.

If at any time Investigator noncompliance is discovered at OHSU, the Sponsor shall promptly either secure compliance or end the Investigator's participation in the study.

Independent audits may be conducted by the Knight DSMC to verify that the rights and well-being of human participants are protected, that the reported trial data are accurate, that the conduct of the trial is in compliance with the protocol and applicable regulatory requirements, that monitoring practices are adequate and in compliance with the monitoring plan, and that evidence of ongoing investigator oversight is present.

11.3 QUALITY ASSURANCE & QUALITY CONTROL

The investigational site will provide direct access to all trial related source data/documents, and reports for the purpose of monitoring by the monitor and/or sponsor, and auditing by the Knight DSMC and/or regulatory authorities.

Quality assurance (QA) auditing activities will occur as detailed in the Knight DSMP. All discrepancies, queries, deviations, observations, and findings will be compiled into a final audit report along with a Corrective and Preventative Action Plan.

The Sponsor-investigator, or study monitor, will verify that the clinical trial is conducted and data are generated, documented (recorded), and reported in compliance with the protocol, GCP, and the applicable regulatory requirements (e.g., Good Laboratory Practices (GLP), Good Manufacturing Practices (GMP)).

12. DATA HANDLING AND MANAGEMENT RESPONSIBILITIES

12.1 SOURCE DATA/DOCUMENTS

The Investigator is responsible for ensuring the accuracy, completeness, legibility, and timeliness of the data reported. All source documents should be completed in a neat, legible manner to ensure accurate interpretation of data. The Investigator will maintain adequate case histories of study participants, including accurate CRFs, and source documentation.

12.2 PARTICIPANT & DATA CONFIDENTIALITY

The information obtained during the conduct of this clinical study is confidential, and unless otherwise noted, disclosure to third parties is prohibited. Information contained within this study will be maintained in accordance with applicable laws protecting participant privacy, including the provisions of the Health Insurance Portability and Accountability Act (HIPAA).

Participant confidentiality is strictly held in trust by the participating Investigator(s) and study team. This confidentiality is extended to cover testing of biological samples and genetic tests in addition to the clinical information relating to participants. Therefore, the study protocol, documentation, data, and all other information generated will be held in strict confidence. No information concerning the study or the data will be released to any unauthorized third party without prior written approval of the sponsor.

The study monitor, other authorized representatives of the sponsor, representatives of the IRB or manufacturer supplying study product may inspect all documents and records required to be maintained by the Investigator, including but not limited to, medical records (office, clinic, or hospital) and pharmacy records for the participants in this study. The clinical study site will permit access to such records.

Upon enrollment, participants will be assigned a code that will be used instead of their name, medical record number or other personally identifying information. Electronic files for data analysis will contain only the participant code. Codes will not contain any part of the 18 HIPAA identifiers (e.g., initials, DOB, MRN). The key associating the codes and the participants' personally identifying information will be restricted to the Investigator and study staff. The key will be kept secure on a restricted OHSU network drive - in a limited access folder.

The study participant's contact information will be securely stored at each clinical site for internal use during the study. At the end of the study, all records will continue to be kept in a secure location for as long a period as dictated by local IRB and institutional regulations. Study participant research data, which is for purposes of statistical analysis and scientific reporting, will be transmitted to and stored within the Knight Cancer Institute per [OHSU's Information Security Directives](#). Individual participants and their research data will be identified by a unique study identification number. The study data entry and study management systems used by clinical sites and by Knight Cancer Institute research staff will be secured and password protected per [OHSU's Information Security Directives](#). At the end of the study, all study databases will be de-identified and archived within the Knight Cancer Institute.

12.3 DATA COLLECTION & STORAGE: PRIVACY, CONFIDENTIALITY & SECURITY

Data collection is the responsibility of the clinical trial staff at the site under the supervision of the site Investigator. The Investigator is responsible for ensuring the accuracy, completeness, legibility, and timeliness of the data reported. Standard institutional practices will be followed as described in the [OHSU's Information Security Directives](#) to maintain the confidentiality and security of data collected in this study. Study staff will be trained with regard to these procedures.

Loss of participant confidentiality is a risk of participation. Efforts will be made to keep study participant identities confidential except as required by law. Participants' samples will be identified by code only and stored in OHSU protocol #4422. Specifically, each consenting participant will be assigned a unique coded identifier consisting of numbers. This identifier will be associated with the participant throughout the duration of their participation in the trial. The coded identifier will also be used to identify any participant specific samples.

Basic accrual tracking information (demographic, consent, visit information) will be captured in OHSU's electronic clinical information research system (eCRIS), hosted on OHSU secure servers and managed by OHSU's information technology group at their data center in downtown Portland, Oregon. Any additional printed documents containing participant identifiers, such as those from the medical record to confirm eligibility, will be filed in binders and kept in a locked, secure location.

Study outcome data will be captured in electronic case report forms (eCRFs) using an electronic data capture (EDC) system, REDCap Cloud. The REDCap Cloud EDC is a web-hosted application hosted by nPhase (located in Encinitas, CA), and is an approved EDC system that has been reviewed by OHSU Security. To further preserve confidentiality, PHI in the EDC system will be limited to just demographics, birth date and visit dates. The web-accessible EDC system is password protected and encrypted with role-based security, and administered by designated informatics staff within OHSU or Knight Cancer Institute. All users of the database are assigned a unique ID, username, and password and must complete training appropriate to their role before they are authorized to enter, access, and store data in the database.

Data from correlative studies will be entered into the RedCap Cloud EDC system by study personnel at OHSU. All other electronic data extracts will be stored only on OHSU computers and restricted drives, limited only to study investigators and staff with authorization to access the data. Quality assurance will be conducted as outlined in Section 11.3, Quality Assurance & Quality Control.

12.3.1 FUTURE USE OF STORED SPECIMENS

Each participant who signs consent will be assigned a unique coded identifier consisting of numbers. This identifier will be associated with the participant throughout the duration of their participation in the trial. The coded identifier will be used to identify any participant specific samples. Blood and bone marrow samples collected for the purposes of this protocol will be stored under OHSU protocol #4422 until they can be analyzed in the [name] Laboratory.

12.4 MAINTENANCE OF RECORDS

Records and documents pertaining to the conduct of this study, source documents, consent forms, laboratory test results and medication inventory records, must be retained by the

Investigator for a period of 2 years following the date a marketing application is approved for the drug for the indication for which it is being investigated; or, if no application is to be filed or if the application is not approved for such indicate, until 2 years after the investigation is discontinued and FDA is notified. No records will be destroyed without the written consent of the Sponsor, if applicable. It is the responsibility of the sponsor to inform the Investigator when these documents no longer need to be retained.

If the Investigator relocates or for any reason withdraws from the study, the study records must be transferred to an agreed upon designee, such as another institution or another investigator at OHSU. Records must be maintained according to institutional or FDA requirements.

12.5 PUBLICATION AND DATA SHARING POLICY

This study will comply with the NIH Public Access Policy, which ensures that the public has access to the published results of NIH funded research. It requires scientists to submit final peer-reviewed journal manuscripts that arise from NIH funds to the digital archive PubMed Central upon acceptance for publication.

This study will adhere to the requirements set forth by the ICMJE and FDAAA that requires all clinical trials to be registered in a public trials registry (e.g., ClinicalTrials.gov) prior to participant enrollment.

12.6 DELIVERY OF PROGRESS REPORTS TO STUDY FUNDER

Upon the request of Janssen Research & Development, LLC, the Institution will submit oral or written reports on the progress of the Study as provided by this protocol. Within one hundred twenty (120) days following the completion or termination of the study, Institution will furnish Janssen Research & Development, LLC with a final report detailing the results of this study.

13. ETHICS/PROTECTION OF HUMAN PARTICIPANTS

13.1 ETHICAL STANDARD

The Investigator will ensure that this study is conducted in full conformity with Regulations for the Protection of Human Participants of Research codified in 45 CFR Part 46, 21 CFR Part 50, 21 CFR Part 56, 21 CFR 312 (for IND studies), 21 CFR 812 (for IDE studies), and/or the ICH E6.

13.2 INSTITUTIONAL REVIEW BOARD

The protocol, informed consent form(s), recruitment materials, and all participant materials will be submitted to the IRB for review and approval. Approval of both the protocol and the consent form must be obtained before any participant is enrolled. Any amendment to the protocol will require review and approval by the IRB before the changes are implemented to the study. All changes to the consent form will be IRB approved; a determination will be made regarding whether previously consented participants need to be re-consented.

13.3 INFORMED CONSENT

Written informed consent will be obtained from all participants, or the legally authorized representative of the participant, participating in this trial, as stated in the Informed Consent section of [21 CFR Part 50](#). If a participant's signature cannot be obtained, and for all participants under the age of 18, the Investigator must ensure that the informed consent is signed by the participant's legally authorized representative. Documentation of the consent process and a copy of the signed consent shall be maintained in the participant's medical record.

13.3.1 CONSENT PROCEDURES AND DOCUMENTATION

Informed consent is a process that is initiated prior to the individual's agreement to participate in the study and continues throughout the individual's study participation. Extensive discussion of risks and possible benefits of participation will be provided to the participants and their families as appropriate. Consent forms will be IRB-approved and the participant will be asked to read and review the document. The Investigator will explain the research study to the participant and answer any questions that may arise. All participants will receive a verbal explanation in terms suited to their comprehension of the purposes, procedures, and potential risks/benefits of the study, alternatives to participation, and of their rights as research participants. Participants will have the opportunity to carefully review the written consent form and ask questions prior to signing. The participants should have the opportunity to discuss the study with their surrogates or think about it prior to agreeing to participate. The participant will sign the informed consent document prior to any procedures being done specifically for the study. The participants may withdraw consent at any time throughout the course of the trial. A copy of the informed consent document will be given to the participants for their records. The rights and welfare of the participants will be protected by emphasizing to them that the quality of their medical care will not be adversely affected if they decline to participate in this study.

13.4 PROTOCOL REVIEW

The protocol and informed consent form for this study must be reviewed and approved in writing by the OHSU Knight Cancer Institute's Clinical Research Review Committee (CRRC) and the appropriate IRB prior to any participant being consented on this study.

13.5 CHANGES TO PROTOCOL

Any modification of this protocol must be documented in the form of a protocol revision or amendment submitted by the Investigator and approved by the CRRC and IRB, before the revision or amendment may be implemented. The only circumstance in which the amendment may be initiated without regulatory approval is for a change necessary to eliminate an apparent and immediate hazard to the participant. In that event, the Investigator must notify the IRB and Sponsor within 5 business days after the implementation.

15. APPENDICES

APPENDIX A: PERFORMANCE STATUS CRITERIA

ECOG Performance Status Scale		Karnofsky Performance Scale	
Grade	Descriptions	Percent	Description
0	Normal activity. Fully active, able to carry on all pre-disease performance without restriction.	100	Normal, no complaints, no evidence of disease.
		90	Able to carry on normal activity; minor signs or symptoms of disease.
1	Symptoms, but ambulatory. Restricted in physically strenuous activity, but ambulatory and able to carry out work of a light or sedentary nature (e.g., light housework, office work).	80	Normal activity with effort; some signs or symptoms of disease.
		70	Cares for self, unable to carry on normal activity or to do active work.
2	In bed <50% of the time. Ambulatory and capable of all self-care, but unable to carry out any work activities. Up and about more than 50% of waking hours.	60	Requires occasional assistance, but is able to care for most of his/her needs.
		50	Requires considerable assistance and frequent medical care.
3	In bed >50% of the time. Capable of only limited self-care, confined to bed or chair more than 50% of waking hours.	40	Disabled, requires special care and assistance.
		30	Severely disabled, hospitalization indicated. Death not imminent.
4	100% bedridden. Completely disabled. Cannot carry on any self-care. Totally confined to bed or chair.	20	Very sick, hospitalization indicated. Death not imminent.
		10	Moribund, fatal processes progressing rapidly.
5	Dead.	0	Dead.

APPENDIX B: SUMMARY OF CAUTIONARY MEDICATIONS

Summary of Cautionary Medications

Category	Drug Name
Strong CYP3A4/5 inhibitors	Voriconazole, Boceprevir, clarithromycin, cobicistat, conivaptan, danoprevir/ritonavir, eltegravir/ritonavir, grapefruit juice, indinavir/ritonavir, itraconazole, ketoconazole, lopinavir/ritonavir, mibefradil, nefazodone, nelfinavir, posaconazole, ritonavir, saquinavir, saquinavir/ritonavir, telaprevir, telithromycin, tipranavir/ritonavir, troleandomycin, voriconazole
Strong CYP3A4/5 inducers	Avasimibe ^{2,3} , carbamazepine, mitotane, naftillin, nevirapine, oxcarbazepine, phenobarbital, phenytoin, primidone, rifabutin, rifampin (rifampicin) ³ , St. John's wort (hypericum perforatum) ³
CYP3A4/5 substrates with NTI¹	Terfenadine, Alfentanil, apixaban (doses >2.5 mg only), aprepitant, astemizole, cisapride, cyclosporine, diergotamine, dihydroergotamine, ergotamine, fentanyl, lovastatin, nicardipine, nisoldipine, pimozide, quinidine, rivaroxaban, simvastatin, sirolimus, tacrolimus, terfenadine, thioridazine
Pgp inducers	Aliskiren, colchicine, dabigatran, digoxin, everolimus, fexofenadine, loperamide, maravirac, posaconazole, ranolazine, saxagliptan, sirolimus, sitagliptin, and tolvaptan

¹ NTI = narrow therapeutic index drugs whose exposure-response indicates that increases in their exposure levels by the concomitant use of potent inhibitors may lead to serious safety concerns (e.g., Torsades de Pointes).

² Herbal product

³ P-gp inducer

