1.3.3.1 Pharmacokinetics in Humans

“The pharmacokinetic characteristics of JNJ-40346527 were assessed in all 3 clinical studies conducted so far. Across studies the following main PK characteristics of JNJ-40346527 following multiple daily oral regimen were observed:

- Rapid absorption following oral administration
- Dose proportional increase of C_{max} (following QD dosing) and AUC (QD and BID dosing)
- Mean terminal half-life (t_½) of ~140 hours
- Dose-related systemic accumulation
- Steady state level reached by ~21 days of dosing
- No apparent sex related differences in PK characteristics
- No impact of food on PK characteristics”^a

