1.3.3.4 Safety in Humans

JNJ-40346527 was generally well tolerated by (i) healthy volunteers, (ii) subjects with active RA, and (iii) subjects with relapsed or refractory HL. The most frequent JNJ-40346527 treatment-emergent adverse events (AEs) are shown in **Table 2.**^a

Table 2. Summary of JNJ-40346527 treatment emergent adverse events^a

Organ system	Treatment emergent AEs
Gastrointestinal:	
• diarrhea,• nausea,• vomiting• constipation,• abdominal pain,• gastroesophageal reflux
Hematologic:	
• anemia,• decrease in WBC (neutrophils, monocytes, lymphocytes),• reticulocytes
Hepatic:	
• AST and ALT increase
Pulmonary:	
• dyspnea
Constitutional symptoms:	
• pyrexia,• headache,• back pain
Laboratory changes:	
• increase in creatinine kinase and lactate dehydrogenase

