5.1.4 COMPATIBILITY

“JNJ-40346527 is a reversible inhibitor of primarily CYP3A4 and CYP2C8 and to a lesser extent of several other CYP isoforms (ie, CYPs 2B6, 2C9, 2C19, and 2D6) in vitro. JNJ-40346527 increased the plasma exposure of midazolam (by ~65%) in a clinical Phase 1 study, suggesting

a weak inhibition of CYP3A4 at clinically relevant doses.

JNJ-40346527 is an inhibitor of P-gp mediated transport of digoxin in vitro but was not a substrate for P-gp in vitro. Care should be taken if JNJ-40346527 is to be administered with P-gp substrates, especially those with narrow therapeutic index. The clinical impact of co-administration of JNJ-40346527 with known inhibitors and inducers of CYP3A4/5, CYP2C8, or CYP2C19 are not fully understood. An increase or decrease of the systemic exposures of JNJ-40346527 and its active metabolites has to be anticipated”^a

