6.4.2 INFECTION PROPHYLAXIS

The use of prophylactic antibacterial, antifungal, and antiviral agents is recommended according

to institutional guidelines.

Note, certain antibiotics may have interactions with specific inhibitors and thus this must be reviewed closely prior to study enrollment and while on study.

Possible prophylaxis includes use of prophylaxis for HSV infection with acyclovir or valacyclovir; levofloxacin for bacterial prophylaxis, as long as patient is not febrile.

The azole isavuconazole can likely be used concurrently with the study drug without dose adjustments. However if other azoles are prescribed such as posaconazole, fluconazole, or voriconazole, caution must be used as prophylaxis and may require measurement of drug levels to monitor dose. Potential interaction of antifungals should be reviewed with an oncology pharmacist and the study PI.

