6.4.5 P-GLYCOPROTEINS (P-GP)

“JNJ-40346527 is an inhibitor of P-gp mediated transport of digoxin in vitro but was not a substrate for P-gp in vitro. Care should be taken if JNJ-40346527 is to be administered with P-

gp substrates" especially those with narrow therapeutic index (e.g., digoxin) and consultation with oncology pharmacist and Investigator is required (Refer to Appendix B for detailed list of agents).

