6.4.6 GASTROINTESTINAL

Anti-emetics, anti-diarrheal agents and acid suppressive therapies should not be taken 2 hours before or after study drug (e.g., antacids, H2 blockers, and proton pump inhibitors) will be prescribed per institutional guidelines.

Study participants may receive anti-emetic therapy as needed during their treatment which may include ondansetron, prochlorperazine, haloperidol and lorazepam.

The use of anti-diarrheals will be administered per investigator's discretion. First line agents such as loperamide and tincture of opium, and/or octreotide can be utilized.

Nonclinical data demonstrates that JNJ-40346527 was not affected by the concomitant intake of medications inducing a pronounced and long-lasting reduction of gastric acid production such as proton-pump inhibitors or histamine H2 receptor antagonists. The use of acid reducing agents will be per investigators discretion.

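### Section 6.4.5 requires a consultation for P-gp substrates and cites Appendix B for the list, but the only P-gp row there, which contains digoxin, is headed 'Pgp inducers'

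*Combined protocol and SAP*

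**What the plan says.** Sections 5.1.4 and 6.4.5 both report that JNJ-40346527 inhibits P-gp transport of digoxin in vitro and is not itself a P-gp substrate in vitro. Section 5.1.4 draws the consequence: "Care should be taken if JNJ-40346527 is to be administered with P-gp substrates, especially those with narrow therapeutic index".

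Section 6.4.5 repeats the caution, gives digoxin as its example of a narrow-index substrate, and adds a required step and a pointer: "e.g., digoxin) and consultation with oncology pharmacist and Investigator is required (Refer to Appendix B for detailed list of agents".

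Appendix B, the table of cautionary medications, has four rows:
- strong CYP3A4/5 inhibitors
- strong CYP3A4/5 inducers
- CYP3A4/5 substrates with a narrow therapeutic index
- 'Pgp inducers'

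The last row begins "Aliskiren, colchicine, dabigatran, digoxin, everolimus, fexofenadine, loperamide" and continues with seven more drugs.

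Two other sections deal with drugs in that row. Section 6.4.6 says of anti-diarrheals, "First line agents such as loperamide and tincture of opium, and/or octreotide can be utilized". Section 6.4.2 covers antifungals, naming posaconazole among others: "Potential interaction of antifungals should be reviewed with an oncology pharmacist and the study PI".

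**The concern.** Section 6.4.5 makes a consultation mandatory and relies on Appendix B to say which drugs trigger it. A coordinator checking a participant's medications at OHSU or at either of the two participating sites (Section 4.3.1) would look there for P-gp substrates and find no row of that name. The only P-gp row names the opposite kind of interaction: drugs that act on P-gp, where the rule concerns drugs that P-gp transports. The protocol attaches no specific rule to P-gp inducers.

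A literal reader could therefore conclude that the drugs in that row need no Section 6.4.5 consultation. At stake is whether a safety instruction is applied consistently to concomitant medication. No efficacy or error-rate question is involved.

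**Working it through.** There is no planned figure to reproduce. The check sets the texts side by side and counts.

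**1. Which class does the rule cover?** Sections 5.1.4 and 6.4.5 both say P-gp substrates. This fits the stated mechanism: the study drug inhibits P-gp, so the drugs at risk are those that P-gp transports. Because the study drug is not a P-gp substrate in vitro, the protocol gives no reason to expect a P-gp inducer to alter its exposure.

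**2. Is there a rule for P-gp inducers elsewhere?** No. The inducer rule in Section 6.4.4 concerns CYP3A4, and the Section 5.1.4 remark on inducers concerns CYP3A4/5, CYP2C8 and CYP2C19.

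**3. What does Appendix B supply?**
- Rows: 4. Rows headed P-gp substrates: 0. Rows headed 'Pgp inducers': 1.
- Drugs in that row: aliskiren, colchicine, dabigatran, digoxin, everolimus, fexofenadine, loperamide, maraviroc, posaconazole, ranolazine, saxagliptin, sirolimus, sitagliptin and tolvaptan (three-row spelling variants aside), which makes 14.

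**4. For how many drugs do the documents show the heading to be wrong?** One. Section 6.4.5 treats digoxin as a substrate and Appendix B lists it under inducers. For the remaining 14 − 1 = 13, no section states P-gp substrate status. That they were meant as substrates is inferred from Section 6.4.5 citing this table as its list.

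**5. How many drugs depend on the heading?** Digoxin is named in Section 6.4.5, so it is caught whatever the heading says. Posaconazole goes to pharmacist and PI review under Section 6.4.2. That leaves at most 14 − 1 − 1 = 12. This is an upper bound, because the Section 6.4.5 rule is written for the class and because other general rules, such as the anticoagulation review in Section 6.4.1, may catch some of them.

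The table's footnotes are not used as evidence. Footnote 3, for P-gp inducers, marks drugs outside the row so headed. But footnote placement is itself doubtful, since the herbal-product mark is on avasimibe and not on St. John's wort.

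**The case against.** The best reply is that a reader would not be misled for long. Section 6.4.5 sends the reader to a four-row table in which one row concerns P-gp, and that row contains the rule's own example. The table's title flags every listed drug for caution. Posaconazole and sirolimus also appear in CYP3A4/5 rows. The operative text in Sections 5.1.4 and 6.4.5 is correct, and it could be read as requiring consultation only for narrow-index substrates. All of this stands and keeps the effect small. It does not make the heading right: a required consultation still cites a list that does not exist under the name of its class.

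A reader might go further and infer a demonstrated safety gap for loperamide, since it is in the row, is a first-line agent in Section 6.4.6, and diarrhea is in Table 2. The documents do not support that:
- No section calls loperamide a P-gp substrate or a narrow-index drug. If it is a substrate within the Section 6.4.5 rule, that rule already applies to it.
- The 2-hour separation from study drug is not the only control. Section 6.4.6 also leaves anti-diarrheals to the investigator's discretion, so what is not repeated there is the pharmacist step.
- Table 2 gives no rates. Section 9.4.1 does, and diarrhea is not among the events reported in 20% or more of participants.

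A reader might also set the 2-hour separation against the mean terminal half-life of about 140 hours (Section 1.3.3.1) and conclude that the separation achieves nothing. That calculation would be unsound. A terminal half-life does not describe the hours around an oral dose of a rapidly absorbed drug, and the protocol nowhere offers the separation as a P-gp control.

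**Conclusion.** The point holds as a labelling error in an operative safety list. The documents prove it for 1 of 14 drugs; for 13 it is inferred, on the assumption that the row was intended as the list that Section 6.4.5 promises. Read literally, the heading removes the drugs other than digoxin from the required consultation, with at most 12 relying on the list alone.

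The practical effect is small, and the clinical size of any interaction cannot be judged from in vitro inhibition. The error is still worth correcting, because the instruction is mandatory and must be applied alike across sites. The Simon two-stage design, power, analyses and DLT rule are untouched.

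**What to change.** Have the study pharmacist confirm the 14 drugs in the row, rename it 'P-gp substrates', and move or remove any drug that is not confirmed.

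Two optional editorial items can go into the same amendment:
- If loperamide is confirmed as a substrate, add a pointer to Section 6.4.5 beside it in Section 6.4.6.
- In Section 5.1.7, change the reference for the medication tables from Appendix C, which covers contraception, to Appendix B.

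The cost is one pharmacist check and one changed heading, plus up to two short text edits. No procedure, data item or participant is added.
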